7.2 Adjustments for Covariates

Not applicable for the primary analyses.

7.3 Handling of Dropouts or Missing Data

Subjects who discontinue the study prior to or after the initiation of the study drug will not be replaced in this study and available data of these subjects until the point of discontinuation will be summarized. For situations with no rules for handling missing data, the default will be no imputation.

7.4 Interim Analyses and Data Monitoring

No interim analysis or data monitoring is planned for this study

7.5 Multi-center Studies and Pooling of Centers

This study will be conducted at approximately 3 centers in United States (US). Data from all centers will be pooled and pooled data will be used for summary tables.

7.6 Multiple Comparisons/Multiplicity

No adjustment for multiplicity will be performed in this study, as there is not statistical analysis planned in this study.

7.7 Active-Control Studies Intended to Show Equivalence

Not applicable to this study.

7.8 Examination of Subgroups

No subgroup analysis will be performed.

8 STATISTICAL ANALYSIS

8.1 Analysis Populations

The study will use following analysis populations for data summarization. Frequency count and percentage of subjects in each analysis population will be summarized.

Population	Definition	Displays
Enrolled Population	The Enrolled Population will consist of all subjects who signed informed consent and have data captured in the clinical database.	Disposition information will be summarized using the Enrolled Population.
Safety Population	The Safety Population will include all subjects who received at least one dose of Flortaucipir F 18 or Florbetapir F 18 injection.	All demographic, baseline and safety endpoints will be using the Safety Population.
ITT Population	The ITT Population will include all subjects in safety population, for whom image data are available i.e. who have a valid Flortaucipir F 18 scan assessment [SUV _r (quantitative) and/or visual reads (qualitative)].	All analyses involving imaging outcomes will be based on the ITT Population.
Per Protocol Population	The Per Protocol Population will include all subjects in ITT population who were classified on Florbetapir positive ($\alpha\beta+$) by either investigator or Avid.	All analyses involving imaging outcomes will be based on the Per Protocol Population.

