7. Are patients who have received a radiopharmaceutical for imaging or therapy within the past 24 hours prior to either imaging session for this study.
8. Have evidence of amyloid deposition as demonstrated by a positive florbetapir F 18 PET scan.
9. Are patients who, in the opinion of the investigator, are otherwise unsuitable for a study of this type.

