7.1.1.1. Screening Florbetapir F 18 PET scan

The screening florbetapir F 18 PET scan is to be performed to assess for evidence of amyloid pathology and should be interpreted by the local reader prior to enrollment. Amyloid scans that have been obtained within 3 years of screening can be submitted for review by the local reader for enrollment criteria. If deemed interpretable, the subject would not need to complete the screening florbetapir F 18 PET scan.

- For women of childbearing potential, a negative pregnancy test must be obtained within 24 hours prior to injection; If screening serum pregnancy test obtained within 24 hours prior to injection, the pregnancy test need not be repeated.
- Height and body weight will be measured prior to injection.
- A physician or licensed/credentialed medical professional (that is, a PET technologist, imaging center nurse, or a regional equivalent) designated by the site principal investigator must see the subject prior to administration of Florbetapir F 18 Injection to determine if they are still suitable to undergo the scan;
- Vital signs will be taken (pulse rate, respiratory rate, supine blood pressure) immediately prior to injection of florbetapir F 18;
- Subjects will receive a single IV bolus injection of approximately 370 MBq (10 mCi) +10% of florbetapir F 18 followed by a saline flush. A 20-minute continuous, dynamic PET brain scan will begin approximately 50 minutes following the dose administration;
- A physician or licensed/credentialed medical professional (that is, a PET technologist, imaging center nurse, or a regional equivalent) designated by

Protocol ¹⁸F-AV-1451-A19: “¹⁸F-AV-1451 PET Imaging in Subjects with Frontotemporal Dementia”

the site principal investigator will see the subject prior to discharge from the imaging center to evaluate the subject’s readiness for discharge;

- A follow-up phone call to the subject, or designated decision maker, will be conducted between 2 or 3 business days of the imaging day, but not before 48 hours post-injection, to confirm subject well-being and to collect information about any new adverse events. If both of these days are not business days, the follow-up phone call can occur the following business day.

7.1.2. **¹⁸F-AV-1451 PET Imaging Visit: Visit 2**

The ¹⁸F-AV-1451 PET scan should be performed at least 16 hours apart from the Florbetapir F 18 PET scan due to the half-life of fluorine 18. The following assessments will be performed for all subjects:

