8.9.1 Qualitative Assessment of Images

The visual read results will be categorized as Not consistent with AD pattern (τ AD-), and AD pattern (τ AD) (τ AD+, τ AD++) for Flortaucipir F 18 PET results. The visual read results will be summarized by frequency count and percentage for the analysis populations (ITT and per protocol)

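### SAP 8.1 builds the Per Protocol Population from florbetapir-positive subjects, whom the protocol excludes, so every subject read negative by both readers is left out

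*SAP*

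**What the plan says.** The Per Protocol row of SAP 8.1 includes "all subjects in ITT population who were classified on Florbetapir positive", and the positive call may come "by either investigator or Avid", so one positive read is enough. The parent ITT set requires a valid flortaucipir assessment (SUVr, visual read or both) and has no amyloid condition.

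Protocol 5.3.2, criterion 8, excludes subjects who "Have evidence of amyloid deposition as demonstrated by a positive florbetapir F 18 PET scan". Protocol 7.1.1.1 says the screening scan "should be interpreted by the local reader prior to enrollment". It also allows an older scan in its place: "Amyloid scans that have been obtained within 3 years of screening can be submitted for review by the local reader for enrollment criteria".

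The SAP 8.1 table gives the same use to both sets. For ITT: "All analyses involving imaging outcomes will be based on the ITT Population". For Per Protocol: "All analyses involving imaging outcomes will be based on the Per Protocol Population". SAP 8.9.1 calls for visual reads on both populations. SAP 8.9.2 calls for SUVr on one *or* the other.

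**The concern.** A per-protocol set normally holds the subjects who met the entry criteria and were studied as planned. Here membership requires the finding that criterion 8 treats as a reason not to enroll.

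This matters because of the question the study asks. The protocol introduction and SAP section 2 both ask whether the regional tau pattern typical of AD appears in FTD. Screening out amyloid-positive subjects helps separate that question from unrecognised AD. A Per Protocol table made up of amyloid-positive or reader-discordant subjects does the reverse: an AD pattern in them could simply reflect AD. An empty table would be questioned at once. A table of one to three subjects under a familiar label might be read as support for, or against, the ITT result.

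**Working it through.** **Inputs.** Per Protocol and ITT definitions: SAP 8.1. Exclusion criterion 8: Protocol 5.3.2. Local read before enrollment: Protocol 7.1.1.1. Enrollment of up to 25: SAP 4.5 and Protocol 8.1.1. The plan states no expected Per Protocol size, so there is no figure to reproduce.

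**Step 1: who can enter.** Take the investigator's classification in SAP 8.1 to be the local read in Protocol 7.1.1.1. The documents do not say this outright. Each subject then falls in one of four cells:

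| Local read | Avid read | Passes criterion 8 on the local read | In Per Protocol as written |
|---|---|---|---|
| negative | negative | yes | **no** |
| negative | positive | yes | yes |
| positive | negative | no | yes, if scanned anyway |
| positive | positive | no | yes, if scanned anyway |

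The only cell that satisfies criterion 8 on both reads is the only one shut out. Subjects in the second row were enrolled under the stated procedure, so they are not necessarily protocol violators. Screen failures cannot fill the set, because ITT requires a flortaucipir assessment.

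**Step 2: does another section correct it?** No. Protocol 8.1.2 has only efficacy and safety populations. SAP 5.2 declares no change from the protocol's analyses. SAP 7.8 rules out subgroup analyses, which argues against a deliberate amyloid-positive subset. The row carries both the word *positive* and a plus sign, so one character lost in text extraction does not explain it.

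**Step 3: how large the set would be.** Let d be the probability that Avid reads a locally negative scan as positive. The documents do not give d; the values below are assumptions. Suppose 25 locally negative subjects all have valid flortaucipir scans and an Avid read, and nobody is enrolled despite a positive local read. The Per Protocol size X is then Binomial(25, d), with

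- E(X) = 25d
- P(X = 0) = (1 − d)^25
- P(X ≤ 1) = (1 − d)^25 + 25d(1 − d)^24

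| d | E(X) | P(X = 0) | P(X ≤ 1) |
|---|---|---|---|
| 0 | 0 | 1 | 1 |
| 2% | 0.5 | 0.98^25 = 0.603 | 0.911 |
| 5% | 1.25 | 0.95^25 = 0.277 | 0.642 |
| 10% | 2.5 | 0.90^25 = 0.072 | 0.271 |

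With X ≤ 1 no standard deviation exists. That affects only the SUVr summary, since visual reads are counts and percentages.

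**Step 4: alternative wordings.** Under *not positive by either reader* the expected size is 25(1 − d): 25, 24.5, 23.75 and 22.5 for the four values of d. Under *negative by either reader*, all 25 subjects enrolled on a negative local read qualify, and the set equals ITT.

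**The case against.** The study is descriptive, with no inferential analysis planned. The protocol's imaging population is everyone with image data, which the SAP's ITT set reproduces, so the primary objective is still answered. The affected tables are supplementary. A very small set would also be visible: SAP 8.1 requires counts for each population, SAP 8.4 tabulates amyloid status, and SAP 8.3 lists protocol deviations. All of this stands and limits the harm. It makes the error easier to notice but does not correct it, and the SAP still orders a visual-read table on that set.

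A second argument is that this is an evident drafting slip, perhaps a dropped *not*, and that a reviewer should not write the rule when intent is unknown. The slip is plausible, but the repair is not self-evident: replacing *positive* with *negative* and keeping *either* gives a set equal to ITT. The sponsor therefore has to say how the two reads combine. It is also fair that removing locally negative, Avid-positive subjects goes beyond the eligibility rule, which rests on the local read. That choice keeps the SAP's own two-reader rule, and it should be labelled an analysis rule.

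Finally, the discordance rates are assumed. They illustrate size only; the contradiction follows from the text without them.

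**Conclusion.** The concern holds. SAP 8.1 contradicts exclusion criterion 8, and nothing in either document resolves it. Programmed as written, the Per Protocol set is empty or consists of subjects enrolled despite a positive read and reader-discordant subjects. The wrong output is the Per Protocol visual-read table, plus the SUVr table if run on that set; the ITT tables stand. The size is 0 of up to 25 with compliance and agreement, and an expected 0.5 to 2.5 subjects at assumed discordance of 2% to 10%. Those figures rest on all 25 having an Avid classification and on none being enrolled with a positive local read. Listing the cells also assumes that the investigator's classification is the local read. Because planned tables depend on the definition and the repair is short, it should be made before any table is produced.

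**What to change.** Reconcile SAP 8.1 with Protocol 5.3.2 and 7.1.1.1, with the sponsor confirming the intended set. Suggested Per Protocol definition:

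> ITT subjects whose eligibility amyloid scan (study florbetapir scan or accepted historical amyloid scan) was not classified as positive by the investigator/local reader or, where an Avid classification exists, by Avid.

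Add that:

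- the Avid read is an analysis rule only and does not alter eligibility;
- a missing or indeterminate Avid read does not by itself remove a subject;
- subjects positive by either reader are listed separately.

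Do not use *negative by either*.

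In the same edit, have SAP 8.9.2 summarise SUVr for ITT *and* Per Protocol. In SAP 8.9, replace Efficacy Population with the population or populations meant; Protocol 8.1.2 defines that term but SAP 8.1 does not.

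The cost is one table row, one word and one term, with no new scans. The sponsor should first confirm that an Avid amyloid classification is recorded: it is named only in SAP 8.1, and both Protocol 8.1 and SAP 7.1 make transfer of eligibility amyloid scans to Avid conditional.

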8.2 Disposition of Subjects

The frequency count and percentage of subjects enrolled, completed and discontinued during the study, as well as the reasons for discontinuation will be summarized.

A listing of all subjects who discontinued the study will be presented in a listing.

8.3 Protocol Deviations/Violations

The protocol deviations will be identified prior to data base lock. Protocol deviations will be derived from the eCRF data or will be obtained from the clinical monitoring reports. The Avid/contract research organization (CRO) will monitor and approve the final protocol list.

A listing of all protocol deviations will be presented.

8.4 Demographic and Other Baseline Characteristics

All demographic and baseline characteristics will be summarized using the safety population.

Age, height, weight (at Florbetapir F 18 imaging visit prior to dose administration), BMI, MMSE Score and MRI volumetric measurement score will be summarized as continuous variables using descriptive statistics.

Birth gender, race, ethnicity, highest level education, subject amyloid status, alcohol and substance history will be summarized as categorical variables using frequency count and percentage.

All demographic and baseline characteristics data will be presented in listings.

8.5 Family History

Family History data will be presented in a listing for the safety population.

8.6 Disease History

Diagnosis of FTD will be summarize according to symptomatic clinical syndrome associated with expected FTD pathology by frequency counts and percentage. A listing related to diagnosis of FTD will be provided.

Disease history will be summarized using descriptive statistics for the subjects in Safety Population, and will include:

- Number of months since symptom onset
- Number of months since diagnosis

For subjects with dates of diagnosis or symptom onset is available, months will be calculated as:

- Months = (Date of screening - Date of symptom onset/diagnosis)/12

For partial symptom onset/diagnosis date, if only the day is missing, then impute the day as the first day of the month; if both the day and month are missing, then impute it as 01 January of the year.

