05 MAY 2016, FINAL

Name of Compound:
¹⁸F-AV-1451 ([F-18]T807)

Sponsor:
Avid Radiopharmaceuticals
Philadelphia, Pennsylvania USA

CONFIDENTIAL

This material is the property of Avid Radiopharmaceuticals (Avid). The information is confidential and is to be used only in connection with matters authorized by Avid and no part of it is to be disclosed to others without prior written permission from Avid.

Protocol ¹⁸F-AV-1451-A19: “¹⁸F-AV-1451 PET Imaging in Subjects with Frontotemporal Dementia”

Sponsor: Avid Radiopharmaceuticals	Name of Compound: ¹⁸ F-AV-1451([F-18]T807)	Active Ingredient(s): 7-(6-[F-18]fluoropyridin-3-yl)-5H-pyrido[4,3-b]indole
Title of Study: ¹⁸ F-AV-1451-A19 “ ¹⁸ F-AV-1451 PET Imaging in Subjects with Frontotemporal Dementia”		
Planned number of subjects (Enrolled): Approximately 25 Subjects diagnosed by a dementia specialist with a clinical Frontotemporal Dementia (FTD) syndrome and expected tau or TDP-43 pathology.		
Name of compound: ¹⁸ F-AV-1451([F-18]T807) Dose: 370 MBq (10 mCi) Route of Administration: Intravenous (IV) bolus		
Study Phase: I		
Study Centers: Approximately 3 centers in the United States		
Trial Objectives: The primary objective of this study is: 
• To evaluate ¹⁸F-AV-1451 retention in PET scans of FTD subjects. A secondary objective of this study is: 
• To expand the ¹⁸F-AV-1451 safety database.		
Eligibility: See Section 5.3, Selection of Subjects.		
Study Design: This is a phase I study that will evaluate imaging characteristics of ¹⁸ F-AV-1451 in subjects with Frontotemporal Dementia (FTD). Subjects followed in a referral center research cohort for FTD will be contacted to participate and must provide informed consent before starting any ¹⁸ F-AV-1451-A19 study procedures. Screening assessments may take place over several days and will include demographic information, a medical assessment for eligibility, ECG, a brief cognitive assessment (e.g. MMSE), and florbetapir F 18 Positron Emission Tomography (PET) imaging. The screening florbetapir F 18 PET scan is to be performed to assess for evidence of amyloid pathology and should be interpreted by a local reader prior to enrollment. Subjects will receive a single IV bolus injection of approximately 370 MBq		

Protocol ¹⁸F-AV-1451-A19: “¹⁸F-AV-1451 PET Imaging in Subjects with Frontotemporal Dementia”

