1. INTRODUCTION

The clinical diagnosis of patients with dementia is challenging and is frequently inaccurate compared to pathological diagnosis at autopsy. Although Alzheimer’s disease (AD) is the most common cause of dementia, other etiologies including Fronto-Temporal Dementia (FTD), vascular dementia and Dementia with Lewy Bodies occur in a substantial number of cases, (Barker et al. 2002) and there may be substantial overlap in the clinical presentation of these disorders. In clinico-pathological studies, 10 - 20% of patients diagnosed with AD in life did not have pathology consistent with the disease at autopsy (Lim et al. 1999, Mayeux et al. 1998, Ranginwala et al. 2008). Conversely, a recent study showed that 40% of dementia patients diagnosed with a disorder other than AD by an expert neurologist in life had AD pathology (i.e., AD or mixed dementia) on post mortem examination (Beach et al. 2012).

Accurate antemortem diagnosis can be particularly challenging in FTD given the clinical and pathologic heterogeneity of the disease (Rabinovici and Miller 2010). Most cases of FTD can be classified into two major pathologic categories: (1) diseases that involve tau deposition (FTD-Tau) and (2) conditions associated with tau-negative, ubiquitin and TDP43-positive inclusions (FTD-TDP) (Mackenzie et al. 2010). In a minority of cases, FTD-Tau can be predicted during life with high accuracy based on the presence of a known mutation in the MAPT gene, or based on a highly correlated clinical phenotype (e.g. progressive supranuclear palsy (PSP) - Richardson’s Syndrome) (Josephs et al. 2006). However, the relationships between other FTD clinical phenotypes and pathologic subtypes are far less predictable (Forman et al. 2006, Hodges et al. 2004, Josephs et al. 2011, Kertesz et al. 2005). For example, the underlying histopathology in patients with behavioral-variant FTD (bvFTD), the most common clinical FTD syndrome, is split equally between FTD-Tau and FTD-TDP (Josephs et al. 2011) and there are currently no known reliable methods to distinguish the two during life. Accurately determining the underlying neuropathology during life is a critical need to enhance the development and testing of biologically specific drugs targeting tau or TDP.

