5.3.1. Inclusion Criteria

Subjects diagnosed by a dementia specialist with symptomatic clinical syndromes with expected Frontotemporal Dementia pathology will be enrolled. Clinical syndromes associated with FTD pathology include: behavioral-variant FTD, FTD with motor-neuron disease, non-fluent/agrammatic and semantic variants of primary progressive aphasia, progressive supranuclear palsy syndrome and corticobasal syndrome. Symptomatic carriers of a known autosomal dominant gene mutation associated with FTD, including: MAPT, GRN, C9ORF72, TARDP, CMP2B, VCP, FUS as well as non-gene carriers are eligible for enrollment.

Diagnosis will be determined by companion study with detailed characterization provided by enrolling physician.

Subjects who are identified with one of the above clinical syndromes of FTD pathology and meet all of the following criteria are eligible to enroll in this trial:

1. Male or female subjects at least 18 years of age;

2. Subjects who give informed consent or have a legally authorized (LAR) to consent for study procedures.
3. Subjects who have volumetric brain MRI images obtained as part of the site’s companion protocol within one year of enrollment available for submission to Avid. (If the subject does not have a prior MRI available for submission to Avid, an MRI may be conducted under this protocol if the subject is able to tolerate one.); and
4. Subjects who in the opinion of the investigator can tolerate the PET scan procedures.

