8.1.1. Sample Size Estimation

This study will enroll up to 25 subjects. This sample size was chosen in order to allow for qualitative and descriptive review of ¹⁸F-AV-1451 PET binding in subjects with clinically defined FTD. Based on prior studies, 10-15 cases are typically

Protocol ¹⁸F-AV-1451-A19: “¹⁸F-AV-1451 PET Imaging in Subjects with Frontotemporal Dementia”

sufficient for preliminary exploratory analysis. The sample size for this study is slightly larger to accommodate the heterogeneous pathology that underlies FTD. Results of the exploratory analysis from this study will permit planning of subsequent, hypothesis-driven studies.

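### Uptake is pooled over all FTD subjects: the SAP drops the protocol's description by clinical diagnosis, and neither document names expected pathology or mutation status as a data item

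*SAP*

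**What the plan says.** **Population.** The protocol synopsis describes subjects by a clinical "Frontotemporal Dementia (FTD) syndrome and expected tau or TDP-43 pathology". The inclusion criteria (protocol 5.3.1) are looser and do not repeat the tau or TDP-43 wording: "symptomatic clinical syndromes with expected Frontotemporal Dementia pathology will be enrolled". They list six clinical syndromes and admit both non-carriers and carriers: "Symptomatic carriers of a known autosomal dominant gene mutation associated with FTD, including: MAPT, GRN, C9ORF72", followed by four further genes.

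**Rationale.** The protocol Introduction says that FTD-Tau can be predicted accurately in life only for a minority of cases, from a MAPT mutation or a closely correlated phenotype such as PSP-Richardson's. Of behavioural-variant FTD (bvFTD), the commonest syndrome, it says that the pathology "is split equally between FTD-Tau and FTD-TDP" and that no reliable method separates the two in life. Protocol 8.1.1 and SAP 4.5 explain the somewhat larger sample by this heterogeneity. Protocol 8.1.1 adds: "Results of the exploratory analysis from this study will permit planning of subsequent, hypothesis-driven studies".

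**Analysis.** Protocol 8.2.1 plans to describe uptake across clinical diagnosis groups, and protocol 8.1 plans baseline tables by clinical group. SAP 7.1 summarises everything as one FTD group, and SAP 7.8 allows no subgroup analysis. SAP 8.9.1 and 8.9.2 tabulate visual reads and SUVr by analysis population only. SAP 5.2 declares no change from the protocol's analyses. Syndrome appears in SAP 8.6: "Diagnosis of FTD will be summarize according to symptomatic clinical syndrome associated with expected FTD pathology", with a listing.

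**The concern.** The sample was enlarged because the pathology is mixed, and the analysis then averages over that mixture. A pooled SUVr summary cannot show whether high and low values fall in subjects whose expected pathology differs. The pooled SD also absorbs any difference between pathology groups, which limits its use for planning a later study that contrasts them.

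The pooled visual read does not recover the information. In the criteria of SAP 6.4.1, absence of neocortical uptake and uptake confined to mesial temporal, anterolateral temporal or frontal regions fall in the same category.

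There is also a plain discrepancy between the documents: a by-diagnosis description that the protocol promises is missing from the SAP and is not declared as a change.

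**Working it through.** **The plan's own figure.** The sample of up to 25 is justified descriptively. No alpha, power, effect size or SD is given, so there is nothing to reproduce.

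**Is expected pathology or mutation status a named item?**

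- Protocol 7.1.1 (screening): disease history covers symptom onset, diagnosis and family history. Neither item is named.
- Protocol 11.2 and SAP 6.1 (flow charts): neither is named.
- SAP 6.3 (screening and baseline assessments): neither is named.
- SAP 8.4 (baseline): "Birth gender, race, ethnicity, highest level education, subject amyloid status, alcohol and substance history will be summarized as categorical variables". Neither is named here or among the continuous variables.
- SAP 8.5 (family history): a listing, and family history is not a genotype.
- SAP 8.6 (disease history): clinical syndrome and months since onset and diagnosis.

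**Is uptake split by anything related to pathology?** Protocol 8.2.1 splits it by clinical diagnosis group. SAP 7.1, 7.8, 8.9.1 and 8.9.2 do not split it. The declaration in SAP 5.2 does not fit this difference.

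**Would syndrome alone be enough?** Only in part. The Introduction gives two routes to a confident expectation of tau. The phenotype route (PSP) can be read from the syndrome. The MAPT route cannot: in the SAP 8.6 summary, a MAPT carrier presenting with bvFTD is counted simply as bvFTD, the syndrome that the Introduction describes as half tau and half TDP.

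**How much precision would a split have?** The documents give no recruitment mix, so every group size below is an assumption. Results are in units of the within-group SD.

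- Even split over six syndromes: 25/6 = 4.2, about 4 each. Half-width of the 95% CI for a mean: t(0.975, 3)/√4 = 3.182/2 = 1.59 SD.
- All 25 pooled: t(0.975, 24)/√25 = 2.064/5 = 0.41 SD.
- Two pathology groups, for the difference in means: t(0.975, n1+n2−2) × √(1/n1 + 1/n2).
  - 12 v 13: 2.069 × 0.400 = 0.83 SD
  - 8 v 17: 2.069 × 0.429 = 0.89 SD
  - 5 v 20: 2.069 × 0.500 = 1.03 SD
  - 4 v 4, the rest indeterminate: 2.447 × 0.707 = 1.73 SD
- Difference detectable with 80% power at two-sided 5% (both assumed; noncentral t): 1.17 SD for 12 v 13 and 1.46 SD for 5 v 20.

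The first three two-group cases assume that every subject can be labelled tau or TDP-43. Given what the Introduction says about bvFTD, that is optimistic. Any such split is therefore descriptive.

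**The case against.** The strongest reply is that the trial did not set itself a tau-versus-TDP test. The primary objective is to evaluate retention, and the purpose singled out in the Introduction is whether the regional pattern typical of AD occurs in FTD. The AD-pattern visual read addresses that without any pathology label. This stands. A reader might infer that without the label no SUVr, high or low, can be interpreted; for the trial's own question that does not follow.

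Second, the information may already exist. Diagnosis comes from a companion study, with detailed characterisation by the enrolling physician. The companion-data transfer in protocol 8.1 and SAP 7.1 is open-ended, all eCRF data are to be listed, and the CRF that the SAP cites is not among the documents. Syndrome and regional SUVr are both listed by subject, so a partial look by syndrome is possible, including at PSP. This also stands. It means that the items are not named, not that they are never recorded, and that the trial is not barred from showing whether retention follows tau. But a listing is not a planned summary, and labels assigned after the scans have been seen are weaker.

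Third, the Introduction names confident predictors for tau only, and only for a minority of cases; it names none for TDP-43. A contrast of confident tau with confident TDP-43 therefore cannot be built from the documents alone or treated as the trial's sole internal check, and the indeterminate group may be large. This limits what the split can deliver, but does not remove the case for it.

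**Conclusion.** The point holds as a reporting gap with a cheap remedy. Neither document names expected pathology or mutation status, no planned uptake summary uses either, and the SAP omits the protocol's by-diagnosis description while declaring no changes. The omission is the firmest part, because it follows from the two texts alone. The change should be made, but the objective and the planned pooled results remain valid without it.

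The size cannot be fixed from the documents. Under an even six-way split, which is an assumption, a syndrome mean carries a half-width of about 1.6 SD. A two-way pathology split gives 0.83 to 1.03 SD for the difference if everyone can be labelled, and worse if many are indeterminate.

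A reader might go further and calculate by how much a later trial would be oversized if planned on the pooled SD. The documents do not support such a figure: it needs an assumed tau–TDP difference, equal groups and a follow-on design contrasting the two, and none of these is given. Without autopsy or another pathology standard, a split by expected pathology is supportive evidence only.

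**What to change.** 1. Restore uptake summaries by clinical diagnosis group in SAP 8.9.1 and 8.9.2, and amend SAP 7.1 and 7.8 to permit them. Otherwise, declare and justify the omission in SAP 5.2.
2. Record for each subject, before the flortaucipir result is known, expected pathology as tau, TDP-43 or indeterminate, with its basis (named mutation or phenotype). The source is the enrolling physician or the companion-study transfer. Record mutation status only where it is already known, with unknown as a category.
3. Add both variables to SAP 8.4. Show visual reads and SUVr by expected pathology, labelled descriptive, with individual values plotted, and let the amended SAP 7.1 and 7.8 cover this split too.

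**Cost.** One or two eCRF or transfer fields, a further set of table columns, one plot and a short SAP amendment. No extra subjects, visits or procedures are needed. Neither document schedules genetic testing, and this change should not add it. The downside is small groups, possibly well under 12, and a sizeable indeterminate category, so the tables should carry no tests and no claim of confirmation.
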